8.6.1.3. Reporting Adverse Events

AEs, whether spontaneously reported by the subject or noted by authorized study personnel, will be recorded in the subject's medical record and on the appropriate AE eCRF. Each recorded AE will be described by its duration (represented in dates), affected eye(s) (if applicable), maximum severity of the AE, seriousness criteria, suspected relationship to the study medication, actions taken with the study medication, and the study participation, outcome of the AE, and any other attributable causes of the AE.

Regardless of relationship to the clinical study, AEs that occur at any time after the subject has provided written informed consent until subject withdrawal or the scheduled exit visit, must be recorded. To improve the quality and precision of acquired AE data, Investigators should observe the following guidelines:

- Whenever possible, use recognized medical terms when recording. Do not use colloquialisms and/or abbreviations.
- If known, record the diagnosis (i.e., disease or syndrome) rather than component signs and symptoms and /or laboratory or test findings (e.g., record congestive heart

failure rather than dyspnea, rales, and cyanosis, and enlarged heart on chest x-ray). However, other events that are considered unrelated to an encountered syndrome or disease should be recorded as individual AEs (e.g., if congestive heart failure and severe headache are observed at the same time and are clinically unrelated, each event should be recorded as an individual AE).

- If the diagnosis is not known, then record the leading component sign, symptom, or test finding and describe the other clinically related findings in the narrative description of the case. A suspected diagnosis can be used and described as such (e.g., record suspected or probable myocardial infarction); this has to be updated in the clinical database once the diagnosis is confirmed.

AEs occurring secondary to other events (e.g., sequelae) should be identified by the primary cause. A primary AE, if clearly identifiable, generally represents the most accurate clinical term. If a primary AE is recorded, events occurring secondary to the primary event should be described in the narrative description of the case. For example:

The subject developed orthostatic hypotension and subsequently fainted and fell to the floor wherein she experienced a head trauma and neck pain.

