The primary AE in this example is orthostatic hypotension. The fall, head trauma, and neck pain should be described in the narrative description of the case.

- For intermittent events (e.g., intermittent headache), the event onset date should be recorded as the date the subject first started to experience the event and resolution date should reflect when the last occurrence resolved or stopped. Separate AEs for each event should not be recorded. For example, if a subject experienced headache on 14SEP2015 lasting for three hours, then subsequently experienced intermittent episodes of headache every day for approximately 3 hours until 21SEP2015, then the AE date of onset is 14SEP2015 and the resolution date is 21SEP2015.
- For intermittent events, record the maximum severity of the individual events. For example, if a subject complains of intermittent headaches for one week and the severity of each headache ranges from mild to moderate, then the severity would be moderate.
- For intermittent hospitalizations occurring for a primary AE (e.g., in a subject with multiple sclerosis, commonly known for its relapsing and remitting course, in some cases leading to multiple hospital confinements), the subsequent hospitalizations should be described in the narrative description of the case.
- If treatment was initiated, include the treatment and duration of the medication(s) in the eCRF.

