8.6.5. Time Period and Frequency for Collecting AE and SAE Information

AEs and SAEs will be monitored for and collected at the time points specified in Schedule of Events and Procedures ([Table 3](#)), from the signing of the ICF until the subject withdrawal or the scheduled exit visit. (Note: Although AEs will be monitored for and collected prior to study medication administration, the statistical data analysis will determine and summarize treatment-emergent AEs, i.e., those AEs that began or worsened in severity after the first study medication administration.)

All SAEs will be recorded and reported to Santen or designee immediately and under no circumstance should this exceed 24 hours, as indicated in [Section 12.4](#), Appendix D. The investigator will submit any updated SAE data to Santen within 24 hours of it being available.

Investigators are not obligated to monitor for new AEs or SAEs after conclusion of the study participation. However, if the investigator learns of any SAE, including a death, at any time after a subject has been discharged from the study, and he/she considers the event to be reasonably related to the study medication or study participation, the investigator must promptly notify Santen.

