4.3. Safety-Related Definitions

4.3.1. Adverse Event

Events reported on the AE electronic Case Report Form (eCRF) will be assessed according to the recently amended Food and Drug Administration regulations 21 CFR Parts 312 and 320.

Under Protocol 012601IN, an AE is defined as any untoward medical occurrence that occurs in a study subject, regardless of the suspected cause and regardless of timing of study medication administration. An *on-study* AE can occur any time after the date of informed consent through the last study visit. An AE will be considered as *treatment-emergent* if the AE occurred on or after the treatment start date up to the 2 days (twice the scheduled dosing interval) after treatment end date. Treatment-emergent AEs are a subset of on-study AEs. Both on-study and treatment-emergent AEs will be recorded, but only treatment-emergent AEs will be tabulated.

The severity of each AE will be graded by the Clinical Investigator as Mild, Moderate, or Severe.

Each AE will be classified into a system organ class (SOC) and coded to a preferred term (PT) using Medical Dictionary for Regulatory Activities (MedDRA), version 23.1 published in 2020.

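### SAP 4.3.1 leaves out worsening from the treatment-emergent AE definition that Protocol 8.6.5 sets for the analysis

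*SAP*

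**What the plan says.** Protocol 8.6.5 states what the statistical analysis will do with AEs: it will summarise "those AEs that began or worsened in severity after the first study medication administration". That definition has two limbs, onset and worsening, and no end date.

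SAP 4.3.1 has one limb. Its test for the treatment-emergent label is whether "the AE occurred on or after the treatment start date up to the 2 days (twice the scheduled dosing interval) after treatment end date". The SAP records a wider class of on-study AEs, which "can occur any time after the date of informed consent through the last study visit", but "only treatment-emergent AEs will be tabulated". SAP 9.1 then sets out the by-arm tables by system organ class and preferred term, and separately lists AEs, SAEs and events of special interest without restricting those listings to treatment-emergent events.

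On how an AE is recorded, Protocol 8.6.1.3 gives each AE one entry for "maximum severity of the AE". For intermittent events "the event onset date should be recorded as the date the subject first started to experience the event", and the site is told not to open a separate entry for each episode.

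On how long AEs are collected, the documents differ. Protocol 8.6.5 collects them "from the signing of the ICF until the subject withdrawal or the scheduled exit visit", and 8.6.1.3 says the same ("until subject withdrawal or the scheduled exit visit, must be recorded"). Footnote d of Protocol Table 3 and of SAP Table 1 runs collection to two weeks after the last dose, when a follow-up call asks about AEs.

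**The concern.** The safety objective is a comparison of DE-126 with timolol. Safety is descriptive, with no testing, so the by-arm AE tables are the main AE comparison. The SAP's rule for entering those tables is narrower than the one the protocol announces, and the SAP does not declare a departure.

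The events at risk are those that first appear after consent and before dosing, and then become worse on drug. If the site keeps a single record, that record has a pre-dose onset date. Under SAP 4.3.1 it is not treatment-emergent, and its on-drug severity is counted in neither arm. A drug that aggravates existing complaints would look somewhat cleaner in the AE tables than the protocol's own definition would show.

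**Working it through.** **1. The two definitions side by side.**

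| | Protocol 8.6.5 | SAP 4.3.1 |
|---|---|---|
| AE begins after first dose | counted | counted, up to last dose + 2 days |
| AE begins before first dose, worsens after | counted | not mentioned |
| End of window | none stated | treatment end date + 2 days |

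SAP 9.1 speaks of tabulating subjects with any AEs, but the explicit rule in 4.3.1 limits what is tabulated. Nothing in SAP section 9 brings worsening back.

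**2. Which AEs fall in the gap.** SAP 4.1.3 defines the treatment start as a date, namely the date of the first dose. Protocol 4.1 puts the first dose at about 20:00 on Day 1. An AE with onset on Day 1 but before that dose is therefore already treatment-emergent. The gap covers onsets from consent to the day before Day 1.

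- Subjects with a separate screening visit: a Screening Period of up to 35 days (28-day washout + 7-day window).
- Subjects who combine Visits 1 and 2: consent and first dose fall on the same date, so the gap is 0 days.

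**3. Whether the record would show the worsening.**

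- Intermittent event: Protocol 8.6.1.3 keeps one entry, the first onset date and the maximum severity. Appendix E sends the severity range to a comment field. Such an AE stays outside the SAP definition.
- Continuous event that worsens: the protocol does not say whether to open a new record. Section 8.6.1.1 treats any significant change since consent as an AE and allows worsening of a pre-existing condition to be one. Appendix D lists exacerbation among the things that qualify. A new record has a post-dose onset and is tabulated; a continued record is not.

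Inclusion therefore depends on site practice.

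**4. The 2-day tail and the post-treatment period.** The stated 2 days reproduces: DE-126 is dosed once daily, so 2 × 24 h = 48 h = 2 days. On timolol's 12 h interval the figure would be 2 × 12 h = 1 day. The SAP applies 2 days to both arms.

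- Completer with last dose on Day 90: the SAP window closes on Day 92. Under footnote d, collection closes on Day 90 + 14 = Day 104. Days outside the tables = 104 − 92 = 12, and 12/104 = 11.5% of recorded days from Day 1. For Visit 5 on Day 83, 12/(83 + 14) = 12/97 = 12.4%. For Day 97, 12/(97 + 14) = 12/111 = 10.8%. If collection ends at the exit visit, the figure is 0.
- Early stopper who stays to Visit 5, as Protocol 7.1 encourages: stopping on Day 14 closes the window on Day 16. With exit on Day 90, 90 − 16 = 74 days are collected but not counted (67 to 81 for exit on Day 83 to Day 97). This follows from Protocol 8.6.5 without footnote d, provided that observational attendance is not treated as withdrawal.

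These are shares of calendar time. The documents give no AE rates, so no number of AEs follows from them.

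**The case against.** The best case for the plan is that the missing phrase changes little. Sections 8.6.1.1 and Appendix D let a site enter a significant worsening as an AE in its own right, and SAP 4.3.1 would then count it. The one-entry rule in 8.6.1.3 is written for intermittent events and does not tell sites to keep a continuous event under its old record. Much of this stands, and it is why the gap is narrow. It does not close the gap: intermittent events are caught by the rule, and for the others the outcome is left to the site.

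A reader might infer that hyperemia aggravated by DE-126 would go unseen, since conjunctival hyperemia was the commonest adverse reaction in the earlier Phase IIb study. The documents do not support that. Hyperemia is graded 0 to 3 at baseline and at each treatment visit, and SAP 9.3 requires by-arm severity frequencies and a tabulation of change from baseline. A shift from mild (1) to severe (3) is 2 units and would also be listed. Only a worsening that resolves between visits could be missed. Symptoms and non-ocular AEs have no such shift table.

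A reader might also take the 11.5% as a share of AEs lost, or the 2-day tail as an error. Neither follows. The percentage is time off drug and holds for completers only if footnote d governs over 8.6.1.3 and 8.6.5. The tail is a legitimate choice, equal in both arms. The later events are still listed under SAP 9.1, and the protocol promises no by-arm post-treatment table.

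**Conclusion.** The omission is real: the SAP's stated rule departs from the definition that the protocol says the analysis will use. Its reach is limited to AEs with onset after consent and before the calendar date of Day 1 that worsen on drug under the same record. It is zero for subjects who combine Visits 1 and 2, and it narrows where sites open a new record or the slit-lamp tables show the sign. The number of AEs affected cannot be computed. No efficacy result is touched, and SAE reporting to the sponsor within 24 hours is unaffected. Severity: minor.

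The lack of a by-arm count for post-treatment AEs is an opportunity to improve reporting and not a defect. The case is strongest for subjects who stop early and are followed to Visit 5. For completers it rests on the unresolved choice between footnote d and the protocol text.

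**What to change.** - In SAP 4.3.1, define treatment-emergent AEs as those that began or worsened in severity on or after the treatment start date, through treatment end date + 2 days.
- Before unmasking, carry out a masked review of all AEs with onset before Day 1 to identify those that worsened on drug. Appendix E asks for a severity range in the comment field only for intermittent or per-administration events, so some records may need a site query.
- If the one-entry rule for intermittent events is to change, so that post-dose worsening gets its own record, do it as a protocol clarification. An eCRF guideline alone should not override Protocol 8.6.1.3.
- Optional: in SAP 9.1 add a separate by-arm count, labelled post-treatment, of AEs, SAEs and suspected adverse reactions with onset more than 2 days after the last dose. State which collection period applies.

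The cost is a line of SAP wording, one masked review and, if the option is taken, one extra table column. No visits are added, and the SAP change needs no protocol amendment. The drawback of the optional count is that some of these events will reflect resumed non-study glaucoma drops, so it should stay apart from the treatment-emergent counts.

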4.3.1.1. Serious Adverse Event

An AE will be counted as a *serious adverse event* (SAE) if the Clinical Investigator selected “Yes” under Item 5 (Is the adverse event serious?) on the AE eCRF. Any AE is considered a SAE if it fulfills one or more of the following criteria:

- Death (i.e., the AE caused or led to death)
- Life threatening (i.e., immediately life-threatening)
- Inpatient hospitalization and/or prolonged hospitalization

- A persistent or significant disability/incapacity (i.e., the AE resulted in a substantial disruption of the subject's ability to carry out normal life functions)
- A congenital anomaly/birth defect in the offspring of a study subject who was exposed to study therapy prior to conception or during pregnancy
- Sight threatening event
- Other medically important event (e.g. requires medical or surgical intervention to prevent one or more of the listed above)

4.3.1.2. Ocular Adverse Event

An AE will be counted as an *ocular AE* if the Clinical Investigator selected “OD”, “OS”, or “OU” under ‘Item 2 (Eye(s) affected)’ on the AE eCRF.

4.3.1.3. Suspected Adverse Reaction

An AE will be counted as a *suspected adverse reaction* (SAR) if the Clinical Investigator selected answered ‘Related’ to the AE eCRF Item 10 (Relationship to Study Drug).

4.3.1.4. Events of Special Interest

Events of special interest (ESI), such as pregnancy, study medication administration error, and AEs leading to study discontinuation or unmasking, will be identified throughout the study.

4.3.2. Safety Measures

Table 4: Safety Assessments Table 4 lists the safety measures to be evaluated for this study.

Table 4: Safety Assessments

Safety Measures	Note
BCVA	BCVA will be measured prior to the 08:00 IOP measurement at all visits except Visit 1 (Screening)/1a (Optional visit) using visual acuity chart (Early Treatment Diabetic Retinopathy Study [ETDRS] chart) and the logMAR scoring. For Visit 1/1a, the corrected visual acuity is performed prior to IOP measurement.
Slit-lamp biomicroscopy: anterior chamber cells anterior chamber flare lid hyperemia lid edema conjunctival (palpebral and bulbar) hyperemia conjunctival chemosis corneal edema	Anterior Chamber Cells will be graded as 0 = No cells, 0.5 = 1-5 cells, 1 = 6-15 cells, 2 = 16-25 cells, 3 = 26-50 cells, or 4 = > 50 cells. Anterior Chamber Flare will be graded as 0 = None, 1 = Faint, 2 = Moderate, 3 = Marked, or 4 = Intense. The other biomicroscopy parameters will be graded as 0 = None, 1 = Mild, 2 = Moderate, or 3 = Severe.

corneal staining (with fluorescein) keratic precipitate lens anterior synechiae of iris posterior synechiae of iris iris color abnormalities eyelash abnormalities eyelid abnormalities	
Ophthalmoscopy glaucomatous optic nerve	Damage to optic nerve will be graded as 0 = None 1 = Mild, 2 = Moderate, 3 = Severe.
Vital signs: systolic blood pressure diastolic blood pressure pulse rate	Systolic blood pressure and diastolic blood pressure will be measured in mmHg. Pulse rate will be measured by beats/minute.

4.4. Other Definitions

4.4.1. Prior and Concomitant Medications

Non-study medications will be categorized into prior medications and concomitant medications. Specifically, the *prior medication* is defined as any non-study medication taken and ended prior to the treatment start date. The *concomitant medication* is defined as any non-study medication taken concurrently while on the study medication, i.e., the treatment period of a concomitant medication taken by a subject's needs to overlap with his/her treatment period of the study medication.

4.4.2. Concurrent Medical Conditions

Concurrent medical conditions are those ongoing conditions or diseases that are present at the signing of informed consent.

5. STUDY POPULATION

Analysis populations utilized for this study are defined below.

The ***Full Analysis Set*** (FAS) includes all randomized subjects who received at least one dose of the study medication (test or control medication) and had at least one post-baseline efficacy assessment of the study eye during the study. This will be the population used for efficacy analyses. Unless specified otherwise, subjects in efficacy analyses are classified by planned treatment, irrespective of the actual treatment received.

The ***Per-Protocol Set*** (PPS) will be a subset of the FAS population, restricted to the subjects who fulfill the protocol in the terms of the eligibility, interventions, and outcome assessment. It will be the analysis population for some sensitivity analyses.

Before the unmasking of treatment assignment, Santen's study team will review all protocol deviations, identify subjects with any protocol deviation that could impact the efficacy outcome, and determine whether or not to exclude the subject or certain data point from the PPS.

The ***Safety population*** will include all randomized subjects who received at least one dose of the study medication. It will be the analysis population for safety analyses to be performed with subjects as treated.

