9.4.2. Full Analysis Set

The FAS will include all randomized subjects who received at least one dose of study medication and provided at least one post-baseline IOP measurement. The efficacy analysis will be performed on the FAS or a subset of the FAS by planned treatment.

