8. EFFICACY ANALYSES

Unless specified otherwise, the efficacy analyses will be performed on the FAS, where subjects are classified by planned treatment, irrespective of the actual treatment received.

Unless specified otherwise, all efficacy analyses will be performed on the study eye, and the data on fellow eye will not be used.

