8.1.2. Sensitivity Analyses

For the primary endpoint and the key secondary endpoints, sensitivity analyses will be performed to assess the robustness of the results from the primary analysis. The following sensitivity analyses will be performed:

- Using the analysis population of the PPS
- Using a pattern-mixture model (PMM) with delta-adjustment approach where missing values are imputed by multiple imputation.

To assess the sensitivity to departure from MAR assumption, a PMM with delta-adjustment will be applied, as follows:

- a. Use Markov chain Monte Carlo (MCMC) to create monotone missingness first. Then obtain standard multiple imputations under MAR assumptions for missing IOP values using monotone regression. The missing data are filled in and 50 complete datasets are created. The seed that will be used in the SAS program is 13546.
- b. For each IOP value that had been missing because of censoring after having received IOP-lowering rescue therapy, or early study discontinuation due to lack of efficacy or AE, these values will adjust by adding delta to the imputed values, where delta = 1.0 mmHg. The seed that will be used in the SAS program is 13546.
- c. Each of the 50 complete datasets will then be analyzed separately using the same MMRM as used for the primary analysis.
- d. The estimates obtained from the MMRM analysis of each complete dataset are combined for inference purposes.
- e. Repeat step b, c, d, with delta = 2.0, 3.0, 4.0, and 5.0 mmHg. The larger the value of delta that is required to reverse the conclusion of the primary analysis, the more robust the conclusion is considered to be.

For the primary endpoint, in addition to the two types of sensitivity analyses described above, if the overall rate of study drug discontinuation due to lack of efficacy or AE is greater than 10% and the difference between the rate in the DE-126 and Timolol arms is greater than 5 percentage points, a trimmed mean analysis ([Permutt et al., 2017](#)) will be conducted as a sensitivity analysis.

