8.2.1. Responder Rates

For binary secondary endpoints, the responder rates will be summarized at each post-baseline visit. Subjects discontinued study by any reason without response will be treated as non-responder. A sensitivity analysis will be conducted by multiple imputing for discontinued subjects with reasons other than AE or lack of efficacy. DE-126/Vehicle arm will be compared with Timolol Maleate arm using Fisher's exact test, and the differences between the two treatment arms will be reported along with 95% CIs.

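### The responder and delta-adjusted analyses default to the FAS, so dosed subjects with no post-baseline IOP are neither counted as non-responders nor imputed

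*SAP*

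**What the plan says.** SAP 5 admits a randomised, dosed subject to the FAS only if the subject "had at least one post-baseline efficacy assessment of the study eye during the study". Protocol 9.4.2 sets the same condition, that the subject "provided at least one post-baseline IOP measurement", and confines efficacy analysis to the FAS or a part of it. SAP 8 then sets the default: "Unless specified otherwise, the efficacy analyses will be performed on the FAS, where subjects are classified by planned treatment".

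Two later sections deal with subjects who leave:

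- SAP 8.2.1, responder rates: "Subjects discontinued study by any reason without response will be treated as non-responder". Its sensitivity analysis uses "multiple imputing for discontinued subjects with reasons other than AE or lack of efficacy".
- SAP 8.1.2, sensitivity analyses for the primary and key secondary endpoints: "Using a pattern-mixture model (PMM) with delta-adjustment approach where missing values are imputed by multiple imputation". The penalty applies to values missing after rescue therapy or after "early study discontinuation due to lack of efficacy or AE, these values will adjust by adding delta to the imputed values". It starts at 1.0 mmHg, and then: "Repeat step b, c, d, with delta = 2.0, 3.0, 4.0, and 5.0 mmHg".

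Neither section names a population other than the FAS. The set of all randomised and dosed subjects exists in SAP 5 as the Safety population, but it is not used for efficacy.

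**The concern.** The first scheduled post-baseline IOP is at Week 2 (Day 14 ± 3). Take two subjects who stop on Day 8 for the same adverse event and then leave the study. One has an IOP taken at an early-termination visit. That reading falls in the Week 2 analysis window, the subject is in the FAS, later visits count as non-response, and later missing values are imputed with delta. The other has no such reading and appears in neither analysis. Attendance at one visit decides this, not outcome.

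Both analyses exist to deal with drop-outs. The FAS rule removes the subjects with the most missing data before either analysis reaches them. Exclusion depends on an event after randomisation, so it can differ between arms. An arm that loses more such subjects shows a higher responder rate and a milder delta-adjusted result than it would with all dosed subjects included.

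**Working it through.** **Inputs from the documents**
- 280 evaluable subjects (140 per arm), 5% drop-out, 294 randomised (147 per arm), SD 4.0 mmHg: SAP 3.3 and Protocol 9.3.1.
- Delta 1.0 to 5.0 mmHg: SAP 8.1.2.
- Upper-limit criteria of 1.5 mmHg at all nine timepoints and 1.0 mmHg at five or more: SAP 8.1.1.1.

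**Assumed inputs**
- k, the number of dosed subjects in an arm with no post-baseline study-eye IOP: 1, 3 or 7.
- FAS responder rate p: 30%, 50% or 70%. The documents give neither k nor p.
- All 147 subjects in the arm are dosed.

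**1. The plan's own figure.** 280 × 1.05 = 294, as stated (280/0.95 = 294.7, or 295, by the other convention). The allowance is 294 − 280 = 14 drop-outs, or 7 per arm. It covers drop-out at any time, so k = 7 would mean that every planned drop-out in the arm left before any reading.

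**2. Responder rate.** With x responders, the FAS rate is p = x/(147 − k). With the k subjects counted as non-responders it is x/147. The overstatement is p − x/147 = p × k/147.

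| k | p = 30% | p = 50% | p = 70% |
|---|---|---|---|
| 1 | 0.2 points | 0.3 | 0.5 |
| 3 | 0.6 | 1.0 | 1.4 |
| 7 | 1.4 | 2.4 | 3.3 |

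For example, 0.70 × 3/147 = 1.4 points.

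A deliberately extreme case puts 7 exclusions in DE-126 and none in timolol. On the FAS, 84/140 (60.0%) against 71/147 (48.3%) gives a difference of 11.7 points and Fisher p = 0.058. With all dosed subjects, 84/147 (57.1%) against 71/147 gives 8.8 points and p = 0.161.

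**3. Delta-adjusted analysis.** If the k subjects were included and all qualified for delta, the arm mean at a timepoint would rise by k × delta/147 from the penalty.

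| k | delta = 1 | delta = 5 |
|---|---|---|
| 1 | 0.01 mmHg | 0.03 mmHg |
| 3 | 0.02 | 0.10 |
| 7 | 0.05 | 0.24 |

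These are upper bounds. Step b gives no delta to a subject lost to follow-up or withdrawing voluntarily. The penalty falls on both arms, so the treatment difference moves only by the imbalance: with 3 qualifying subjects in one arm and 1 in the other, at delta 5, (3 − 1) × 5/147 = 0.07 mmHg.

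**4. Scale.** At the planned SD and a true difference of 0, the expected upper 95% limit at one timepoint is 1.96 × 4.0 × √(2/140) = 0.94 mmHg, before any gain from baseline adjustment. That is 0.06 below the 1.0 mmHg criterion and 0.56 below the 1.5 mmHg margin.

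**5. Primary MMRM.** It uses observed values. A subject with no post-baseline IOP contributes no outcome, so adding the subject leaves the estimates essentially unchanged.

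**The case against.** Three stronger readings are tempting, and the documents do not support them.

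- *The SAP contradicts itself.* The any-reason rule in 8.2.1 sits under SAP 8, whose default is the FAS. It can be read as covering drop-outs within the FAS. Protocol and SAP also agree on the FAS definition.
- *The treatment failures leave the denominator.* The example of lack of efficacy in Protocol 7.1 is a high IOP after randomisation. A subject identified that way normally has a post-baseline study-eye reading and stays in. Those lost are early adverse-event, withdrawal or lost-to-follow-up cases who were never measured again. Nothing in the documents shows that these are mostly intolerance. For the earlier dose-finding study, Protocol 2.2 describes all concentrations as well tolerated and reports three patients with adverse events leading to discontinuation.
- *The effect is large.* Several provisions shrink the group. Protocol 7.1 and SAP 3.4 call for early-termination assessments where possible, and these include IOP. Protocol 7.1 also encourages subjects who stop the drug to attend the remaining visits. The Week 2 analysis window opens at Day 2 (SAP 4.1.6), and a single reading is enough for the FAS. If every early leaver has one, k = 0 and nothing changes.

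It is also fair to say that the responder endpoints lie outside the fixed testing sequence, and that a wider set departs from Protocol 9.4.2.

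These points limit the size but do not close the gap. Early-termination assessment is only to the extent possible, Protocol 7.2 foresees loss to follow-up, and neither 8.1.2 nor 8.2.1 says what happens to a dosed subject with no reading.

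**Conclusion.** The concern holds as a gap between the drop-out rules and the population they run on. It is a low-cost improvement rather than a serious flaw. The likely effect on an arm's responder rate is about a point or less. It reaches 3.3 points only if all 7 planned drop-outs in an arm leave unmeasured and the FAS rate is 70%. The between-arm difference is affected only so far as exclusions are unequal or the responder rates differ.

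No confirmatory claim rests on the responder rates. The delta-adjusted analysis supports the non-inferiority claim, so the omission matters somewhat more there. Even so, 0.10 mmHg for k = 3 needs the largest delta and all three subjects leaving for an adverse event or lack of efficacy. Its full effect on the treatment difference also needs no matching loss in the other arm. The direction is unknown, which is a reason to settle the population before unmasking.

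**What to change.** State in SAP 8.2.1 and 8.1.2 that the responder and delta-imputation analyses include all randomised subjects who received at least one dose, by planned arm. Either replace the FAS for these two analyses, recorded as a departure from Protocol 9.4.2, or add them as supplementary analyses beside the FAS versions. The second choice keeps the effect of the population separate from the effect of delta.

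For subjects with no post-baseline IOP:

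- In the main responder analysis, count them as non-responders. The existing multiple-imputation sensitivity analysis can then apply by reason for leaving, as already written.
- In the delta analysis, impute from baseline IOP and arm, and add delta only in the circumstances that step b already lists. The rule should stay tied to the reason for study discontinuation, not the reason for stopping the drug.

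Report the number excluded from the FAS by arm and reason, so that a reader can see k directly. Keep the FAS for the primary and key secondary MMRM.

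The cost is a short addition to two SAP sections, a note on the departure from the FAS wording in Protocol 9.4.2 and SAP 5, and one disposition table. No new data are needed. Responder rates may fall slightly.
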